12. Uncontrolled hypertension as defined by systolic BP  $\geq 160 \text{ mm Hg}$  or diastolic BP  $\geq 100 \text{ mm Hg}$ , medical intervention indicated, and more than one drug or more intensive therapy than previously used indicated.
13. Poorly controlled diabetes mellitus, in the opinion of the investigator, for example
  - 1) Hb A1c  $>9.0\%$  within 12 weeks prior to randomization (in the medical history);
  - 2) short-term hyperglycemia leading to hyperosmolar or ketoacidotic crisis; and/or
  - 3) history of diabetic cardiovascular complications.
14. Subjects who have major organ damage, including:
  - a. Liver disease with ALT or AST  $>3 \times \text{ULN}$ ; direct bilirubin  $>3 \times \text{ULN}$  with proportion of direct/total bilirubin  $>0.3$ ; or history/evidence of cirrhosis, liver transplant, or presence of clinically significant mass/tumor.
  - b. Heart disease, heart failure as classified by the New York Heart Association classification 3 or higher, or significant arrhythmia requiring treatment, or recent

myocardial infarction within 6 months of randomization, or significant cardiac iron overload.

- c. Severe lung disease, including pulmonary fibrosis or pulmonary hypertension, i.e.,  $\geq$ Grade 3 NCI CTCAE version 5.0.
- d. Significant kidney disease as indicated by, for example, estimated glomerular filtration rate  $<45$  mL/min/1.73 m^2 (per Modification of Diet in Renal Disease formula).

15. Subjects who have received chronic systemic glucocorticoids  $\leq$ 12 weeks prior to randomization ( $\geq$ 5 mg/day prednisone or equivalent). Physiologic replacement therapy for adrenal insufficiency is allowed.

16. Major surgery  $\leq$ 8 weeks prior to randomization.

17. A history of a clinically significant allergic reaction or hypersensitivity, as judged by the investigator, to any drug or any component of the study drug formulations used in the study (see Investigator's Brochure).

18. History or current malignancies (solid tumors and hematological malignancies) unless the subject has been free of the disease (including completion of any active or adjuvant treatment for prior malignancy) for  $\geq$ 5 years. However, subjects with the following history/concurrent conditions are allowed if, in the opinion of the investigator, the condition has been adequately diagnosed and is determined to be clinically in remission, and the subject's participation in the study would not represent a safety concern:

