Urinalysis assessments include: appearance, color, pH, specific gravity, ketones, protein, glucose, bilirubin, and urobilinogen, including occult blood and microscopic examination of sediment (only if occult blood is detected).

Shift tables will be used to summarize the shift from Baseline grade to maximum CTCAE grade (Grade 1 to 4 and Missing) for selected hematology and chemistry parameters listed in Appendix 4, by treatment arm and the combined IMR-687 treatment arms and presented separately for each population. Any subject with a post-Baseline result meeting the criteria, including those collected at unscheduled visits, will be included in the tabulation.

Potentially clinically significant (PCS) Criteria for hepatic function and renal function are shown in Table 5 below. The number and percentage of subjects meeting these PCS criteria will be summarized for hepatic function parameters (ALT, AST, ALP, and total bilirubin), the renal function parameter (serum creatinine), and platelet count separately. Any subject with any post-baseline result (including "unscheduled" visits) meeting the criteria will be included in the tabulation.

Table 5 PCS Criteria for Hepatic Function, Renal Function, and Platelet Count

Hepatic Function	Renal Function	Platelet Count

 ○ Post-baseline Alanine Aminotransferase (ALT) $\geq 3 \times$ upper limit of normal (ULN) ○ Post-baseline Aspartate Aminotransferase (AST) $\geq 3 \times$ ULN ○ Post-baseline Direct Bilirubin (BILDIR) $\geq 2 \times$ ULN ○ Post-baseline ALT/AST and BILDIR (ALT $\geq 3 \times$ ULN or AST $\geq 3 \times$ ULN) and BILDIR $\geq 2 \times$ ULN (Hy's Law) 	
 ○ Post-baseline Creatinine Clearance (CREATCLR) $< 0.5 \times$ baseline ○ Post-baseline Serum Creatinine (CREAT) $> 2 \times$ baseline 	
 ○ Post-baseline Platelet Count $> 1000 \times 10^9/L$

The following figures will be provided for the following hematology, chemistry, and coagulation results: MCV, platelets, neutrophils, reticulocyte (absolute and percent), GGT, LDH, creatinine, AST, ALT, indirect bilirubin, ACR.

- Shift plot from baseline to post-baseline maximum value for each parameter by treatment arm and for the combined IMR-687 treatment arms;
- Box and whisker plot for each lab parameter by visit for each treatment arm and the combined IMR-687 treatment arms.

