13.6.2.3 Vital Signs

Descriptive statistics (N, mean, SD, median, Q1, Q3, minimum, and maximum) will be used to summarize vital sign parameters (body temperature, systolic blood pressure, diastolic blood pressure, heart rate, and respiratory rate) at Baseline, each post-Baseline visit, and change from Baseline to each post-Baseline visit, by treatment arm and the combined IMR-687 treatment arms, for both populations. Study Baseline as defined in Section 10.1.2 will be used.

Potentially clinically significant (PCS) post-baseline vital signs can be identified using the criteria shown in the table below. The number and percentage of subjects with any post-baseline treatment-emergent potentially clinically significant vital sign value will be tabulated by treatment group for each criterion. Any subject with a post-baseline result meeting the criteria, including those collected at unscheduled visits, will be counted.

Potentially clinically significant (PCS) post-baseline vital signs can be identified using the criteria shown Table 6 below. The number and percentage of subjects with any post-baseline treatment-emergent potentially clinically significant vital sign value will be tabulated by treatment arm and the combined IMR-687 treatment arms and will be provided separately for each population for each criterion. Any subject with a post-baseline result meeting the criteria, including those collected at unscheduled visits, will be counted.

Table 6 PCS Criteria for Vital Signs

Vital Signs	
Parameter	Criteria
Heart Rate	
 • ≤ 50 and decrease ≥ 15 bpm • ≥ 100 bpm and increase ≥ 15 bpm • ≥ 120 and increase ≥ 15 bpm
SBP	
 • ≤ 90 and decrease ≥ 20 mm Hg • < 140 mmHg and increase ≥ 20 mmHg • ≥ 140 mmHg and increase ≥ 20 mmHg • ≥ 160 and increase ≥ 20 mm Hg
DBP	
 • ≤ 50 and decrease ≥ 15 mm Hg • < 100 mmHg and Increase ≥ 20 mmHg • ≥ 100 mmHg and Increase ≥ 20 mmHg • ≥ 100 mmHg and increase ≥ 15 mm Hg

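### The direct-bilirubin safety count, and the bilirubin half of the Hy's Law row, ignore baseline although entry admits subjects already at or above the threshold

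*SAP*

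**What the plan says.** SAP 13.6.2.2 tabulates PCS laboratory values against Table 5. The counting rule is "Any subject with any post-baseline result" that meets a criterion, unscheduled visits included. The four hepatic rows are absolute multiples of the upper limit of normal:

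- ALT at or above 3 x ULN
- AST at or above 3 x ULN
- "Post-baseline Direct Bilirubin (BILDIR) $\geq 2 \times$ ULN"
- a combined row labelled Hy's Law: ALT or AST at or above 3 x ULN together with direct bilirubin at or above 2 x ULN

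No hepatic row has a baseline condition, and no baseline count is shown beside it. The paragraph above the table says that the counts "will be summarized for hepatic function parameters (ALT, AST, ALP, and total bilirubin". Table 5 has no row for ALP or total bilirubin and uses direct bilirubin instead.

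Protocol 8.2, exclusion 14a, excludes ALT or AST above 3 x ULN. For bilirubin it excludes direct bilirubin above 3 x ULN only "with proportion of direct/total bilirubin" above 0.3.

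Other PCS displays in the SAP do take account of baseline. The renal criteria in the same table are multiples of the subject's own baseline. SAP 13.6.2.3 counts "any post-baseline treatment-emergent potentially clinically significant vital sign value", and each criterion there includes a change. SAP 13.6.2.4 reports the QTcF threshold counts for both baseline and post-baseline.

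**The concern.** For ALT and AST the PCS threshold coincides with the entry limit, so a subject who enters within the limit has to reach or cross it to be counted. For direct bilirubin the PCS threshold (2 x ULN) lies below the entry limit (3 x ULN, and then only with a raised ratio). The gap between the two admits subjects who are PCS cases on the day they are randomized. The plan foresees liver involvement at entry: SAP 13.4 tabulates hepatic co-morbidity due to iron overload as a baseline characteristic in TDT.

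Safety is the primary objective. A row that mixes pre-existing with new elevations carries background counts that dilute a real effect, and a chance imbalance at baseline can look like a treatment difference in small arms. The combined row matters more because of its label: a reader will take a Hy's Law entry as a new event, while its bilirubin half may pre-date the first dose.

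The analyte mismatch is a separate defect in the same paragraph. A programmer cannot satisfy both the text and the table.

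**Working it through.** The plan gives no figure to reproduce here, so the check applies the two rules to the same subjects. The baseline sample is taken to satisfy the entry limits.

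**Rules, in multiples of ULN**

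- Entry (Protocol 8.2, 14a): excluded if ALT or AST > 3, or if direct bilirubin (DB) > 3 and direct/total > 0.3.
- Counting (SAP Table 5): DB row if DB ≥ 2; ALT row if ALT ≥ 3, and the same for AST; Hy's Law row if (ALT or AST ≥ 3) and DB ≥ 2.

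**Step 1: subjects whose values do not change**

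| ALT | DB | Direct/total | Eligible | In DB row | In Hy's Law row |
|---|---|---|---|---|---|
| 1.0 | 1.9 | 0.20 | yes | no | no |
| 1.0 | 2.0 | 0.20 | yes | yes | no |
| 1.0 | 2.5 | 0.40 | yes | yes | no |
| 1.0 | 3.0 | 0.40 | yes | yes | no |
| 1.0 | 3.1 | 0.40 | no | – | – |
| 1.0 | 4.0 | 0.25 | yes | yes | no |
| 2.9 | 2.5 | 0.40 | yes | yes | no |
| 3.0 | 2.5 | 0.40 | yes | yes | yes |
| 3.1 | 2.5 | 0.40 | no | – | – |

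Unchanged eligible subjects enter the DB row at any value from 2 to 3 x ULN, and above 3 x ULN when the ratio is 0.3 or less. They reach the ALT, AST or Hy's Law rows only at exactly 3.0 x ULN for the transaminase.

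**Step 2: a transaminase rise with bilirubin unchanged**

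ALT from 1.0 to 3.2 with DB fixed at 2.5: counted under Hy's Law, although the bilirubin part was already met. ALT from 2.9 to 3.0 with DB fixed at 2.5: 3.0/2.9 = 1.034, so a 3.4% rise completes the row.

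**Step 3: size**

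Let q be the share of subjects with baseline DB at or above 2 x ULN. The documents do not give q, so 2% to 20% is an assumed range. With n subjects in an arm, the expected number of unchanged subjects in the DB row is n × q, and the chance of at least one is 1 − (1 − q)^n. Arm sizes are those in SAP 8.1.1 and 8.1.2: 30 active, 20 placebo (TDT), 15 placebo (NTDT).

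| q | n = 30 | n = 20 | n = 15 |
|---|---|---|---|
| 2% | 0.6; 45.5% | 0.4; 33.2% | 0.3; 26.1% |
| 5% | 1.5; 78.5% | 1.0; 64.2% | 0.75; 53.7% |
| 10% | 3.0; 95.8% | 2.0; 87.8% | 1.5; 79.4% |
| 20% | 6.0; 99.9% | 4.0; 98.8% | 3.0; 96.5% |

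Each such subject is 1/30 = 3.3, 1/20 = 5.0 or 1/15 = 6.7 percentage points of the arm.

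**The case against.** The strongest reply is that the plan already looks at the liver relative to baseline. The laboratory incidence endpoint listed as primary in SAP 9.0 is a worsening in CTCAE grade, not Table 5. Shift tables from baseline grade to maximum grade cover ALT, AST and blood bilirubin, and Appendix 4 grades these against baseline when baseline is abnormal. ALT and AST have shift plots. Change from baseline is summarized for chemistry, which includes direct bilirubin, and all values are listed by subject. Randomization makes the extra counts equal between arms in expectation, and there is a placebo column. Exclusions 1 and 21 also let the investigator keep out subjects with worrying laboratory values.

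Most of this stands, and it limits the point. What it leaves open is narrow. Appendix 4 has no direct-bilirubin row, the bilirubin shift plot is for indirect bilirubin, and no display shows baseline status for the combined criterion. A reader would have to go to the listings to learn whether a counted case was new.

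A reader might go further and infer that unchanged subjects fill the Hy's Law row. They do not: apart from the single value 3.0 x ULN, the transaminase has to rise. A reader might also infer that both elevations must come from the same sample. Table 5 is silent on timing, and with TDT chemistry scheduled six-weekly from Week 6 a same-sample rule could miss a case whose two elevations fall at different visits. That is a trade-off, not an error.

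**Conclusion.** The point holds for one of the four hepatic rows in full and for the Hy's Law row in part. Direct bilirubin at or above 2 x ULN is counted without regard to baseline, and eligible subjects can already be there. The bilirubin component of Hy's Law can pre-exist for the same reason.

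The size cannot be fixed from the documents. It rests on the baseline prevalence q, and the 2% to 20% range above is an assumption. Per subject it is 3.3 to 6.7 percentage points in arms of 30 to 15.

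The stronger conclusions that the primary laboratory endpoint is affected, or that the rule favours or penalizes IMR-687, are not supported: the primary incidence endpoint requires worsening, and the extra counts are non-differential in expectation. The cost is dilution and the risk of chance imbalance. Applying the criterion to total bilirubin, as the text suggests, would not remove the problem, because entry sets no stand-alone limit on total bilirubin.

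**What to change.** In SAP 13.6.2.2 and Table 5:

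1. Tabulate each hepatic PCS count split by whether the criterion was met at baseline. The QTcF table, which reports baseline as well as post-baseline counts, is the nearest precedent. Baseline-met subjects stay visible but are no longer read as new.
2. For each Hy's Law case, flag separately whether the ALT/AST component and the bilirubin component were met at baseline, and give the dates of the two elevations. The flag has to be per component: a subject entering at ALT 2.9 and direct bilirubin 2.5 x ULN does not meet the combined criterion at baseline, so a split on the combined row alone would still show that subject as wholly new. Showing the timing avoids imposing a same-sample rule.
3. Reconcile the analytes named in the text (ALT, AST, ALP, total bilirubin) with those in Table 5 (ALT, AST, direct bilirubin).

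The cost is SAP wording, one extra column and one derived flag. The counts shown as treatment-emergent will be slightly smaller. The change does not deal with a subject who enters just below 2 x ULN and crosses it through ordinary variation; that subject is still shown as new.

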13.6.2.3 Vital Signs

Descriptive statistics (N, mean, SD, median, Q1, Q3, minimum, and maximum) will be used to summarize vital sign parameters (body temperature, systolic blood pressure, diastolic blood pressure, heart rate, and respiratory rate) at Baseline, each post-Baseline visit, and change from Baseline to each post-Baseline visit, by treatment arm and the combined IMR-687 treatment arms, for both populations. Study Baseline as defined in Section 10.1.2 will be used.

Potentially clinically significant (PCS) post-baseline vital signs can be identified using the criteria shown in the table below. The number and percentage of subjects with any post-baseline treatment-emergent potentially clinically significant vital sign value will be tabulated by treatment group for each criterion. Any subject with a post-baseline result meeting the criteria, including those collected at unscheduled visits, will be counted.

Potentially clinically significant (PCS) post-baseline vital signs can be identified using the criteria shown Table 6 below. The number and percentage of subjects with any post-baseline treatment-emergent potentially clinically significant vital sign value will be tabulated by treatment arm and the combined IMR-687 treatment arms and will be provided separately for each population for each criterion. Any subject with a post-baseline result meeting the criteria, including those collected at unscheduled visits, will be counted.

Table 6 PCS Criteria for Vital Signs

Vital Signs	
Parameter	Criteria
Heart Rate	
 • ≤ 50 and decrease ≥ 15 bpm • ≥ 100 bpm and increase ≥ 15 bpm • ≥ 120 and increase ≥ 15 bpm
SBP	
 • ≤ 90 and decrease ≥ 20 mm Hg • < 140 mmHg and increase ≥ 20 mmHg • ≥ 140 mmHg and increase ≥ 20 mmHg • ≥ 160 and increase ≥ 20 mm Hg
DBP	
 • ≤ 50 and decrease ≥ 15 mm Hg • < 100 mmHg and Increase ≥ 20 mmHg • ≥ 100 mmHg and Increase ≥ 20 mmHg • ≥ 100 mmHg and increase ≥ 15 mm Hg

A plot will be presented to show the pattern of the SBP and DBP values over time by treatment arm and the combined IMR-687 treatment arms. Mean and SE will be presented in the plot. Additionally, spaghetti plots for SBP and DBP values over time will be provided for 1) individual subjects with maximum post-baseline SBP increased ≥ 20 mmHg and SBP ≥ 150 mmHg and 2) maximum post-baseline DBP increased ≥ 20 mmHg and DBP ≥ 100 mmHg. A shift plot displaying shifts from Baseline heart rate ≤ 100 to maximum heart rate >100 post-Baseline will be provided for each population.

All vital signs will be listed in a data listing. All vital sign tables and listings will be reported on the Safety Analysis Set.

13.6.2.4 12-lead ECGs

The average of triplicate 12-lead ECGs will be performed to evaluate the change from Baseline in ECG parameters (heart rate, PR interval, RR interval, QRS duration, QT interval, and QTcF interval). Descriptive statistics (N, mean, SD, median, Q1, Q3, minimum, and maximum) of ECG parameters will be presented for Baseline, each post-Baseline visit, and change from Baseline to each post-Baseline visit by treatment arm, and the combined IMR-687 treatment arms, for both populations. Study Baseline defined in Section 10.1.2 will be used. At Baseline and Week 3 (TDT Population)/Week 4 (NTDT Population), descriptive statistics will also be presented for change from pre-dose to post-dose. All measurements, including those during unscheduled visits, will be provided in data listings, but only the scheduled measurements will be included in the summary.

The average of the ECG results by visit and parameter will be calculated if two or more of the triplicate ECG values are reported at the visit for baseline or post-baseline visits.

The number of subjects whose baseline or post-baseline QTcF values have exceeded the selected Criteria below, will be summarized with the number and percentage of subjects meeting each criterion, by treatment arm, and the combined IMR-687 treatment arms, and visit (baseline, post-baseline), separately for each population. Subjects with baseline or post-baseline (including unscheduled visits) results meeting any criteria will be counted.

Table 7 PCS Criteria for ECGs

ECGs	Criteria
Parameter	Criteria
QTcF Interval	
 • > 450 msec (males only) • > 470 msec (females only) • > 500 msec
QTcF Interval Increase from Baseline	
 • ≥ 30 msec • ≥ 60 msec

All ECG parameters will be listed in a data listing. All ECG tables and listings will be reported using the Safety Analysis Set.

13.6.2.5 Physical Examinations

All physical examination findings will be listed in by-subject listings on the Safety Analysis Set. No tabulation summaries will be provided.

13.6.3 Imputation Methods for Endpoints

Unless otherwise specified, no imputation of data relating to the primary endpoint of safety and tolerability, or for secondary or exploratory efficacy endpoints, will be performed.

13.6.3.1 Pooling of Sites

There will be no pooling of sites.

13.6.4 Efficacy Analyses (Secondary Endpoints)

The PP Analysis Set will be used for all efficacy endpoint analyses. Selected analyses will be repeated on the mITT and/or ITT Analysis Sets as sensitivity analyses, with mITT only used if different than the ITT. The TDT and NTDT populations will be summarized separately for all analyses.

Table 8 Secondary Endpoints – TDT Population

Secondary Endpoints	Time Points	Secondary Endpoint Analysis
Proportion of subjects with a $\geq 20\%$ reduction in RBC transfusion burden with a reduction of at least 2 units of RBCs (hematological improvement)	Fixed time periods of Week 12 to Week 24, Week 24 to Week 36, and Week 12 to Week 36, compared to the 12-week interval prior to Baseline (Day 1)	
 • Cochran-Mantel Haenszel (CMH) analysis: Odds ratios (OR) (active arms vs. placebo), 2-sided 95% CI, p-value • Summary of number and percentage of responders with difference in proportions (active arm-Placebo) and corresponding 2-sided 95% CI • Forest plots of ORs, 2-sided 95% CIs, p-value – Higher dose vs. placebo, Lower dose vs. placebo
Proportion of subjects with a $\geq 33\%$ reduction in RBC transfusion burden with a reduction of at least 2 units of RBCs (hematological improvement)		
Proportion of subjects with a $\geq 50\%$ reduction in RBC transfusion burden with a reduction of at least 2 units of RBCs (hematological improvement)		
Proportion of subjects with a $\geq 20\%$ reduction in RBC transfusion burden with a	Rolling 12-week time periods –	

reduction of at least 2 units of RBCs (hematological improvement)	Day 2 to 85, Day 3 to 86, etc. through Day 170 to Day 253 (Week 36), compared to the 12-week interval prior to Baseline (Day 1)	
Proportion of subjects with a $\geq 33\%$ reduction in RBC transfusion burden with a reduction of at least 2 units of RBCs (hematological improvement)	Rolling 14-week time periods – Day 2 to 99, Day 3 to 100, etc. through Day 156 to Day 253 (Week 36), compared to the 12-week interval prior to Baseline (Day 1)	
Proportion of subjects with a $\geq 50\%$ reduction in RBC transfusion burden with a reduction of at least 2 units of RBCs (hematological improvement)	Baseline to Week 24, Baseline to Week 36	
 Summary statistics of the number of cumulative transfusions at every 3 weeks post-Baseline from Week 3 through Week 36. Analysis of Covariance (ANCOVA) analysis with Baseline value as a covariate: LSMean (95% CI), LSMean difference (95% CI) between each active dose and placebo, and p-value. Plots of the mean number of transfusions, mean number of units, and mean Hb by time periods (Weeks 1-12, Weeks 13-24, Weeks 25-36)
Number of transfusion events	Baseline to Week 36	
Change from Baseline for mean iron chelation therapy daily dose and mean serum ferritin	Baseline to Week 36	
 Analysis of Covariance (ANCOVA) analysis with Baseline value as a covariate: LSMean (95% CI), LSMean difference (95% CI) between each active dose and placebo, and p-value.
The plasma PK profile of IMR-687 after administration to subjects will be evaluated by determination of PK parameters (e.g., C_{max} , t_{max} , AUC_{0-24}) based on drug concentration levels in plasma obtained over time	Baseline and Week 3 (TDT) Baseline and Week 4 (NTDT)	Descriptive summary

Table 9 Secondary Endpoints – NTDT Population

Secondary Endpoints	Time Points	Secondary Endpoint Analysis
Change from Baseline for iron chelation therapy daily dose and serum ferritin	Baseline to Week 36	
 Analysis of Covariance (ANCOVA) analysis with Baseline value as a covariate: LSMean (95% CI), LSMean difference (95% CI)

		between each active dose and placebo, and p-value.
Change from Baseline in mean Hb values at Weeks 12 to 24 and Weeks 24 to 36 in the absence of transfusions [using Hb from Laboratory Hematology] Change from Baseline in mean HbF values at Weeks 12 to 24 and Weeks 24 to 36 in the absence of transfusions	Baseline to Week 12-24, and Week 24-36	
 Summary statistics for the Baseline, post-Baseline, and change from Baseline Hb and HbF by treatment arm Scatter box-whisker plots for mean change over continuous 12-week intervals ANCOVA analysis with Baseline value as a covariate: LSMean (95% CI), LSMean difference (95% CI), and p-value.
Proportion of subjects with an increase from Baseline of $\geq 3\%$ in mean HbF values at Weeks 12 to 24 and Weeks 24 to 36 in the absence of transfusions.	Week 12 to Week 24, and Week 24 to Week 36	
 Cochran-Mantel Haenszel (CMH) analysis: Odds ratios (OR) (active arms vs. placebo), 2-sided 95% CI, p-value Summary of number and percentage of responders with difference in proportions (active arm-Placebo) and corresponding 2-sided 95% CI Forest plots of ORs, 2-sided 95% Cis, p-value – Higher dose vs. placebo, Lower dose vs. placebo
Proportion of subjects with an increase from Baseline of ≥ 1.0 g/dL in mean Hb values at Weeks 12 to 24 and Weeks 24 to 36 in the absence of transfusions. [using Hb from Laboratory Hematology]	Week 12 to Week 24, and Week 24 to Week 36	
 Cochran-Mantel Haenszel (CMH) analysis: Odds ratios (OR) (active arms vs. placebo), 2-sided 95% CI, p-value Summary of number and percentage of responders with difference in proportions (active arm-Placebo) and corresponding 2-sided 95% CI Forest plots of ORs, 2-sided 95% Cis, p-value – Higher dose vs. placebo, Lower dose vs. placebo
Proportion of subjects with an increase from Baseline of ≥ 1.5 g/dL in mean Hb values at Weeks 12 to 24 and Weeks 24 to 36 in the absence of transfusions. [using Hb from Laboratory Hematology]	Week 12 to Week 24, and Week 24 to Week 36	
 Cochran-Mantel Haenszel (CMH) analysis: Odds ratios (OR) (active arms vs. placebo), 2-sided 95% CI, p-value Summary of number and percentage of responders with difference in proportions (active arm-Placebo) and corresponding 2-sided 95% CI Forest plots of ORs, 2-sided 95% Cis, p-value – Higher dose vs. placebo, Lower dose vs. placebo
The plasma PK profile of IMR-687 after administration to subjects will be evaluated by determination of PK parameters (e.g., C_{max} , t_{max} , AUC_{0-24}) based on drug concentration levels in plasma obtained over time	Baseline and Week 3 (TDT) Baseline and Week 4 (NTDT)	Descriptive summary

